RESEARCH TRIAL PROTOCOL

Title: A Digital Twin Smart Educational Platform for Simulating Physical Obstacles and Safe Navigation Training for the Visually Impaired

Principal Investigator: [[name]]

Affiliation: [King Salman center for Disability Research]

Trial Sponsor/Approval Body: Directorate of Special Education, Ministry of Education,
Jeddah, Saudi Arabia.

IRB Approval Reference: JED-SE-2026-ETH-096

Protocol Version & Date: 1.2

1. General Information

- **Protocol Title:** A Digital Twin Smart Educational Platform for Simulating Physical Obstacles and Safe Navigation Training for the Visually Impaired
- **Principal Investigator:** [[name]]
- **Affiliation:** [King Salman center for Disability Research]
- **Trial Sponsor/Approval Body:** Directorate of Special Education, Ministry of Education, Jeddah, Saudi Arabia.
- **IRB Approval Reference:** JED-SE-2026-ETH-096
- **Trial Registration Identifier:**
- **Protocol Version & Date:** Version 1.2 – June 2026.

2. Project Summary and Objectives

The purpose of this clinical/educational trial is to evaluate the spatial orientation and mobility (O&M) efficacy of a dynamic non-invasive digital rehabilitation prototype. The platform bridges high-fidelity urban engineering modeling with adaptive instructional scaffolding to accelerate independent walking safety for visually impaired people (VIP).

Primary Objectives:

- To evaluate if adaptive virtual twin training lowers physical contact failure events during outdoor real-world urban navigation.
- To benchmark the execution latency of multi-modal binaural sound rendering and vibrotactile hardware actuators.
- To document behavioral technology acceptance vectors (TAM) across the target demographic group.

3. Study Design and Methodology

3.1 Trial Design

- **Structure:** A prospective, single-blind, randomized, two-arm parallel interventional controlled study.
- **Allocation Ratio:** (1:1) balanced random partition into an Experimental Arm and a Active Control Arm.
- **Blinding:** Single-blind. Participants are unaware of which training methodology is classified as the novel paradigm. Double-blind execution is implemented during post-intervention field score assessments via independent evaluation observers.

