3.2 Participant Recruitment and Selection

- **Recruitment Channel:** Institutional databases through partnership networks at the Directorate of Special Education and local blind associations in Jeddah.

Inclusion Criteria:

[figure not shown]
- Adults aged between 18 and 60 years old legally diagnosed with severe visual impairment or total blindness.
- Ability to walk unassisted for a minimum continuous duration of 15 minutes.
- Proficiency in screen-reader accessibility controls on smartphone user interfaces.

Exclusion Criteria:

- Co-occurring profound sensorineural hearing loss (preventing 3D spatial binaural discrimination).
- Active upper/lower-limb motor neuropathies disrupting haptic micro-actuator detection.
- Diagnosed vestibular syndromes or severe motion sickness history.

4. Intervention and Execution Plan

[Recruited Sample: N = 30 VIP]

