6.2 Analysis Plan

- **Data Integrity:** Data anonymization is achieved via alphanumeric key mapping (e.g., VIP_JED_01). Missing data points will be addressed using multiple imputation mechanisms.
- **Hypothesis Testing:** Group mean differences will be verified using an Independent Samples (t)-test. Longitudinal skill growth across the 10 sessions will be tracked via a Two-Way Repeated Measures Analysis of Variance (**ANOVA**), setting statistical significance thresholds at an absolute value of ($\alpha = 0.05$). All calculations will run natively within SPSS or Python scipy libraries.

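### Neither the allocation nor the planned t-test accounts for total blindness versus severe visual impairment, leaving a material but avoidable risk of chance imbalance at N = 30

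*Protocol*

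**What the plan says.** All places are in the Protocol; no SAP was available.

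- **Allocation (section 3.1):** "1:1) balanced random partition into an Experimental Arm and a Active Control Arm". No stratification, blocking or minimisation factor is named, and the text does not say what is balanced beyond the ratio.
- **Eligibility (section 3.2):** participants are "legally diagnosed with severe visual impairment or total blindness". The expected share of each is not given.
- **Sample (opening of section 4):** "Recruited Sample: N = 30 VIP".
- **Objective (section 2):** the first primary objective is whether training "lowers physical contact failure events during outdoor real-world urban navigation". Section 6.1 lists the real-world collision rate (RCR) among the primary metrics.
- **Analysis (section 6.2):** "Group mean differences will be verified using an Independent Samples (t)-test", with alpha 0.05. The repeated-measures ANOVA concerns growth over the ten sessions. Neither method names visual status or a baseline value.
- **Baseline (section 5.1):** trials at baseline are mentioned, but what they measure is not stated.

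**The concern.** The outcome is contact with obstacles, and the eligible group runs from people who may have some usable sight to people who have none. It is reasonable to expect the two groups to differ in collisions whatever training they receive, although the Protocol does not say so. The legal diagnosis is an entry criterion, so the status is known before allocation and costs nothing extra to record.

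With about 15 people per arm, chance alone can put noticeably more totally blind participants in one arm. A t-test on raw group means has no term to correct for that. At stake are the credibility of the estimated RCR difference in the one trial that is run, and precision in a sample that has little to spare.

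**Working it through.** The Protocol gives no imbalance figure, power, effect size or SD, so there is no figure of its own to reproduce.

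**Inputs**
- From the Protocol: N = 30 (section 4); 1:1, read as 15 v 15 (section 3.1); alpha 0.05 (section 6.2), taken as two-sided because sidedness is not stated.
- Assumed: K, the number totally blind, lies between 6 and 24 (20% to 80%). D, the difference in mean collisions between totally blind and severely impaired participants, is 0.5 to 1.0 within-group SD.

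**Step 1. Chance of imbalance.** With 15 per arm, the number x of totally blind participants in one arm is hypergeometric:

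P(x) = C(15, x) × C(15, K − x) / C(30, K), and the gap between arms is |2x − K|.

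For K = 15, C(30,15) = 155,117,520.
- Gap 1 (8:7): 2 × 6435² / 155,117,520 = 0.534, so P(gap ≥ 3) = 0.466.
- Gap 3 (9:6): 2 × 5005² / 155,117,520 = 0.323, so P(gap ≥ 5) = 0.466 − 0.323 = 0.143.

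| Totally blind, of 30 | P(gap ≥ 3) | P(gap ≥ 5) |
|---|---|---|
| 6 or 24 | 0.169 | 0.017 |
| 9 or 21 | 0.427 | 0.109 |
| 10 or 20 | 0.245 | 0.050 |
| 12 or 18 | 0.264 | 0.060 |
| 15 | 0.466 | 0.143 |

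The figures jump because the gap has the same parity as K: for even K, a gap of 3 or more means 4 or more. Three of 15 is 20 percentage points and five of 15 is 33. Had allocation been by simple coin toss, the chance of a gap of 20 points or more would be 18% to 36% for K = 6 to 15 (simulated, 200,000 runs).

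**Step 2. Effect on the estimate.** Shift in the arm difference = (gap / 15) × D.
- Gap 3: 0.20 × 0.5 = 0.10 SD; 0.20 × 1.0 = 0.20 SD.
- Gap 5: 0.333 × 0.5 = 0.17 SD; 0.333 × 1.0 = 0.33 SD.

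**Step 3. Effect on the test.** The type I error of the unadjusted t-test was simulated conditional on the gap (K = 15, 40,000 runs per case):

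| Gap | D = 0.5 | D = 1.0 |
|---|---|---|
| 1 (8:7) | 4.5% | 3.1% |
| 3 (9:6) | 5.2% | 5.2% |
| 5 (10:5) | 6.5% | 9.9% |

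The test is conservative when the arms happen to match, close to nominal at 9:6 and inflated at 10:5. Averaged over all allocations, randomisation keeps the nominal rate.

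**Step 4. Precision.** At K = 15 the unadjusted variance is 1 + D²/4 in within-group units, and visual status explains (D²/4) / (1 + D²/4) of it: 0.0625/1.0625 = 6% for D = 0.5 and 0.25/1.25 = 20% for D = 1.0. With 15 per arm and 80% power the t-test detects 1.06 SD. Removing 20% of the variance lowers that to 1.06 × √0.80 = 0.95 SD.

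**Step 5. With stratification.** Permuted blocks of at most 4 within each stratum (assumed size) cap the gap in totally blind participants at 2, that is 2/15 = 13 points. A gap of 20 points or more is then practically ruled out.

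**The case against.** Much of the case on the other side stands.

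- **A reader might infer that a serious imbalance is likely.** The numbers do not support that. The 47% belongs to an even mix, the highest of those tried, where 9:6 or worse means anything beyond the smallest possible split. Other mixes fall to 17%, and a gap of 5 or more never exceeds 14%.
- **A reader might infer that the trial's test is invalid.** It is not. Overall type I error is preserved, and even conditional on 9:6 it stays near 5%.
- **A reader might infer that a collision difference could never be separated from visual status.** Nothing in the Protocol prevents a baseline table by diagnosis or an adjusted analysis, so that goes too far.
- **That residual vision drives collisions is not in the documents.** It is plausible, but D is an assumption, and no RCR scale, mean or SD is given to anchor it.
- **The Protocol is silent on stratification rather than ruling it out.** The word used for the partition is undefined, and an SAP that is not shown might add covariates.

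The last point only partly answers the concern. Stratification has to be in place before the first allocation, and section 3.1 is where it would be set; an SAP cannot supply it afterwards. On the analysis side, section 6.2 already names an unadjusted test, so adding visual status would change the stated method rather than fill a gap.

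**Conclusion.** The point holds as an inexpensive improvement to the design and analysis, not as an error that undermines the trial. A status known at entry is ignored by both the stated allocation and the stated between-arm test. At 15 v 15 the chance of a gap of 20 points or more is roughly one in six to just under one in two, depending on a mix that the Protocol does not give; 33 points or more is uncommon. The consequence is a conditional bias of 0.10 to 0.33 SD when such gaps occur, and some lost precision throughout. The imbalance probabilities rest on 15 per arm and K between 6 and 24. The bias and precision figures rest in addition on D of 0.5 to 1.0 SD; if visual status had no bearing on collisions, both would vanish.

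**What to change.** 1. In section 3.1, stratify the allocation list on total blindness versus severe visual impairment: two strata, permuted blocks of random size, with the list concealed from the trainers.
2. In section 6.2, replace the t-test for RCR with a linear model containing arm and visual status. Add baseline RCR if the baseline trials mentioned in section 5.1 measure it, and state whether they do.

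If allocation has already begun, the second change can still be made and deals with the conditional bias and most of the precision loss by itself.

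**Cost.** A two-stratum list and one or two covariates, using a diagnosis already collected. Each arm may end one or two participants away from 15 (with blocks of at most 4, an excess of 2 in both strata would give 17 v 13). Block ends are slightly predictable, which random block sizes limit. Residual degrees of freedom fall from 30 − 2 = 28 to 27, or to 26 with baseline RCR.

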3.2 Participant Recruitment and Selection

- **Recruitment Channel:** Institutional databases through partnership networks at the Directorate of Special Education and local blind associations in Jeddah.

Inclusion Criteria:

[figure not shown]
- Adults aged between 18 and 60 years old legally diagnosed with severe visual impairment or total blindness.
- Ability to walk unassisted for a minimum continuous duration of 15 minutes.
- Proficiency in screen-reader accessibility controls on smartphone user interfaces.

Exclusion Criteria:

- Co-occurring profound sensorineural hearing loss (preventing 3D spatial binaural discrimination).
- Active upper/lower-limb motor neuropathies disrupting haptic micro-actuator detection.
- Diagnosed vestibular syndromes or severe motion sickness history.

4. Intervention and Execution Plan

[Recruited Sample: N = 30 VIP]

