4.1 The Experimental Arm (AMRLE Group)

Participants assignment code: Adaptive Multi-modal Reality Learning Environment (**AMRLE**).

- **Regimen:** 10 sessions distributed over 5 consecutive weeks (2 sessions per week). Each session lasts 25 minutes.
- **Environment:** Trainees walk inside a safe lab tracking frame wearing open-ear headphones and a custom Bluetooth-enabled 4-zone haptic belt.
- **Execution:** The backend logic tracks user location via an Octree spatial partition mesh. The AI updates environmental complexity (C_{t+1}) using real-time collision loops. The layout dynamically spawns physical blockades (e.g., Jeddah sidewalk construction gaps, unexpected street bins), forcing cognitive adjustments.

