4.2 The Control Arm (Conventional Technology Group)

- **Regimen:** 10 sessions over 5 weeks (2 sessions per week, 25 minutes per session).
- **Environment:** Traditional indoor/outdoor spatial orientation tracks.

- **Execution:** Trainees receive conventional manual orientation and mobility (O&M) rehabilitation. This includes walking on fixed paths using standard white canes, combined with verbal description spatial audio scripts and layout orientation blueprints. No adaptive virtual elements are utilized.

5. Ethical Considerations and Safety Monitoring

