6.1 Assessment Instruments

- **Primary Metrics (System Telemetry):** Digital records capturing Time-to-Task Completion (**TTC**), Real-world Collision Rate (**RCR**), and Path Deviation Index (**PDI**).
- **Secondary Metrics (Psychometrics):** Post-trial deployment of a validated 5-point Likert Scale Technology Acceptance Model (TAM) instrument tracking perceived usefulness and ease of use.

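### The technology-acceptance conclusion should be limited to the screen-reader-proficient adults enrolled, and TAM should also be collected from AMRLE users who stop early

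*Protocol*

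**What the plan says.** Protocol section 2 lists three primary objectives, the third being "To document behavioral technology acceptance vectors (TAM) across the target demographic group". The target group is not defined there or anywhere else. The only population named in the section comes from the purpose statement, which says the platform is meant to "accelerate independent walking safety for visually impaired people (VIP"), with no qualifier about technology skill.

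Section 3.2 sets the entry criteria. One is "Adults aged between 18 and 60 years old legally diagnosed with severe visual impairment or total blindness"; another is "Proficiency in screen-reader accessibility controls on smartphone user interfaces". No reason is given for the second. Two of the exclusions in the same section, on hearing loss and on limb neuropathy, do carry a stated reason.

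Section 6.1 places acceptance among the secondary metrics and describes it as "Post-trial deployment of a validated 5-point Likert Scale Technology Acceptance Model (TAM) instrument tracking perceived usefulness and ease of use". No other TAM time point is given. Section 5.1 gives participants the right to exit. Section 5.2 lists reactions such as vertigo, lag-related sickness and panic under a heading that includes discontinuation. Section 6.2 assigns missing data to multiple imputation without further detail.

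**The concern.** Two selections act on the acceptance result.

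The first is at entry. Many criteria narrow a sample, but this one selects on skill with an assistive digital interface when the outcome is acceptance of an assistive digital platform. People already at ease with such interfaces may well find a new one easier to use. No analysis of the 30 enrolled can recover the ratings of those not admitted. Section 4 already labels the sample simply as 30 visually impaired people, so the restriction could easily drop out of the conclusion as well.

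The second is at exit. Someone who stops using the platform because it made them dizzy or anxious has a strong view of it. If TAM is given only at the end, that view may go unrecorded and the reported acceptance would come from those who tolerated the system.

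At stake is the population to which objective 3 applies, and how completely the platform's actual users are represented. The comparison of collision, time and path outcomes between arms is not at stake, because the criterion applies equally to both arms before randomisation.

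**Working it through.** The protocol states no TAM estimate, precision target, share of proficient people or dropout rate, so there is no figure to reproduce. The check sets the passages side by side and then shows what assumed inputs would imply.

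**Step 1: population.** Section 2 names visually impaired people. Section 3.2 enrols those aged 18 to 60, with severe impairment or blindness, and proficient with a smartphone screen reader. The enrolled group is a subset of the named group, and one of the restricting traits plausibly relates to the outcome.

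**Step 2: use of the skill.** In the experimental arm, "Trainees walk inside a safe lab tracking frame wearing open-ear headphones and a custom Bluetooth-enabled 4-zone haptic belt". No participant-operated smartphone is described in either arm. Screen readers are otherwise mentioned only in section 5.1, for the format of the information sheets. The text therefore gives no purpose for the criterion, although it does not rule one out.

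**Step 3: number of platform users.** N = 30 (section 4) at 1:1 (section 3.1) gives 30 / 2 = 15 per arm. In the control arm, "No adaptive virtual elements are utilized". Acceptance of the platform therefore rests on about 15 people.

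**Step 4: entry selection.** Let p be the share of the wider group that is proficient, and d the mean TAM difference, proficient minus non-proficient. Then

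mean(enrolled) − mean(all) = (1 − p) × d.

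Both inputs are assumptions:

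| p | d = −0.5 | d = 0 | d = +0.5 | d = +1.0 |
|---|---|---|---|---|
| 0.3 | −0.35 | 0 | +0.35 | +0.70 |
| 0.5 | −0.25 | 0 | +0.25 | +0.50 |
| 0.7 | −0.15 | 0 | +0.15 | +0.30 |
| 0.9 | −0.05 | 0 | +0.05 | +0.10 |

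**Step 5: exit selection.** Let f be the share of exposed AMRLE users without a rating, and g the completers' mean minus the mean the others would have given. Then

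mean(completers) − mean(all exposed) = f × g.

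With an assumed f = 3/15 = 0.2, g = 1 gives 0.2 × 1 = 0.2 points and g = 2 gives 0.2 × 2 = 0.4 points. With g = 0 there is no shift, and a negative g reverses it.

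**Step 6: scale.** The 95% half-width of a mean is t(n−1) × SD / √n. With an assumed SD of 0.6 to 1.0, this is 0.33 to 0.55 points for n = 15 (and 0.22 to 0.37 for n = 30). Shifts of the assumed size could thus be comparable to sampling error.

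**Step 7: what imputation could do.** TAM has no earlier measurement. Session telemetry could enter an imputation model, but its link to platform acceptance could be estimated only from AMRLE users who were rated. If only completers are rated, early stoppers' scores are filled in from people who tolerated the system.

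**The case against.** The strongest reply is that the target group is undefined and can be read as the eligible population of section 3.2. On that reading objective 3 and the sample agree. This stands to the extent that there is no proven contradiction, but the term then still needs the definition proposed below.

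A reader might infer that the trial will overstate acceptance. The documents do not support this. They contain neither p nor d, and the table includes zero and negative shifts. Upward is the likelier direction, as a judgement about technology skill and ease of use, and no more than that.

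A reader might also infer that the proficiency criterion is unnecessary and should be deleted. That argues from silence. Section 4.1 is a short summary; it mentions "wearing open-ear headphones and a custom Bluetooth-enabled 4-zone haptic belt" but names no control interface or paired device. Whether to keep the criterion is a debatable eligibility trade-off for the sponsor.

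On timing, giving TAM after use is ordinary, since a platform cannot be rated before it has been tried, and no baseline is needed. Section 6.1 does not say that early stoppers go unrated. Section 5.2 describes halting the system and recovery, without saying that the participant leaves the trial. The exclusion of vestibular disorders and severe motion sickness makes such stops less likely, and an analysis plan not seen here may cover the matter. All of this stands, and it is why the point says that early leavers may give no rating. What remains is that the only stated time point is after the trial, exits are foreseen, and imputation is a weak substitute for a questionnaire that can simply be given earlier.

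**Conclusion.** The point holds as a cheap improvement. The TAM result supports a conclusion about screen-reader-proficient visually impaired adults aged 18 to 60, whereas objective 3 is worded for a wider or undefined group. This is a limit on generalisability. The stated schedule also leaves AMRLE users who stop early at risk of being unrated, and imputation would then rely on completers' scores alone.

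Both selections probably raise the score, but neither sign nor size follows from the documents. The positive shifts shown, up to 0.70 points at entry and 0.2 to 0.4 at exit, rest wholly on assumed shares and score gaps. It would go too far to say that acceptance in the target group cannot be documented: that holds only if the group means visually impaired people in general, which the wording of section 2 suggests but does not state.

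**What to change.** (a) In section 2, restate objective 3, and the conclusion to be drawn from TAM, as applying to screen-reader-proficient visually impaired adults aged 18 to 60. Alternatively, give the reason for the proficiency criterion in section 3.2, or reconsider it.

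(b) In section 6.1, have TAM administered at each participant's last contact, including at early stopping, once at least one AMRLE session has taken place. Report it for all exposed AMRLE participants.

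The cost is protocol wording and earlier use of the same questionnaire for the few who stop. The downside is a narrower stated claim and possibly a slightly less favourable acceptance score.

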4.1 The Experimental Arm (AMRLE Group)

Participants assignment code: Adaptive Multi-modal Reality Learning Environment (**AMRLE**).

- **Regimen:** 10 sessions distributed over 5 consecutive weeks (2 sessions per week). Each session lasts 25 minutes.
- **Environment:** Trainees walk inside a safe lab tracking frame wearing open-ear headphones and a custom Bluetooth-enabled 4-zone haptic belt.
- **Execution:** The backend logic tracks user location via an Octree spatial partition mesh. The AI updates environmental complexity (C_{t+1}) using real-time collision loops. The layout dynamically spawns physical blockades (e.g., Jeddah sidewalk construction gaps, unexpected street bins), forcing cognitive adjustments.

4.2 The Control Arm (Conventional Technology Group)

- **Regimen:** 10 sessions over 5 weeks (2 sessions per week, 25 minutes per session).
- **Environment:** Traditional indoor/outdoor spatial orientation tracks.

- **Execution:** Trainees receive conventional manual orientation and mobility (O&M) rehabilitation. This includes walking on fixed paths using standard white canes, combined with verbal description spatial audio scripts and layout orientation blueprints. No adaptive virtual elements are utilized.

5. Ethical Considerations and Safety Monitoring

